8.4 End of Study

The end of the study is defined as the last visit of the last patient undergoing the study.

9 RADIOTRACER AND IMAGING

9.1 Radiotracer product details

[¹⁸F]FPIA is a radiotracer which is used in PET imaging. All PET imaging and therefore all handling of [¹⁸F]FPIA will occur at either an Imperial College Healthcare NHS Trust or Imperial College London Facility. Recruitment sites will not handle [¹⁸F]FPIA.

9.1.1 Supply Packaging and Labelling

Due to the short half-life of [¹⁸F]FPIA, supply will be on a per-patient basis.

[¹⁸F]FPIA will be packaged, labelled and distributed by an appropriate courier to sites by the University College London GMP facility.

Labels will be prepared in accordance with Good Manufacturing Practice Annex 13 requirements and local regulatory guidelines.

9.1.2 Dispensing and Accountability

[¹⁸F]FPIA will be dispensed as per local practice at the Imperial College London or Imperial College Healthcare NHS Trust Facility and only by staff authorised to do so by the principal investigator.

[¹⁸F] activity will be measured using a calibrator according to the working instructions at the site. Volumes will be adjusted to avoid counter saturation.

Unused [¹⁸F]FPIA will be reconciled, accounted for and disposed of by the Imperial College London or Imperial College Healthcare NHS Trust Facilities according to local guidelines.

Radiotracer accountability records will be maintained throughout the course of the study and filed with delivery documentation.

The investigators are responsible for ensuring that deliveries of the tracer and study material are correctly received, recorded, handled and stored safely and properly, in accordance with regulatory guidelines (ICH-GCP and Good Manufacturing Practice (GMP) and used in accordance with this protocol.

9.2 Imaging Protocol

[¹⁸F]FPIA PET/CT imaging will occur at an Imperial College Healthcare NHS Trust or Imperial College London Facility

Patients taking part in this study will have whole body [¹⁸F]FPIA PET/CT imaging on each of 3 scan visits (baseline/4-6 weeks post therapy/ 12 weeks post therapy (± 4 weeks)). Patients will receive a dose of [¹⁸F]FPIA on each of the 3 scan days.

- Patients will attend the site imaging facility on the scan day.
- Pre-scan assessments will be carried out as per Table 1.
- A small cannula will be inserted into a vein in an arm and a blood sample taken for carnitine testing.
- At 60 minutes prior to the planned PET scan start time, the patient will be injected with a maximum administered activity 370 MBq [¹⁸F]FPIA in a suitable upper limb vein. The administration will be followed by a saline flush.
- After an uptake period of approximately 50 minutes, the patient will be asked to void urine and made comfortable on the scanner bed.
- At approximately 55minutes after injection of [¹⁸F]FPIA, the patient will undergo a low-dose whole body CT scan, (skull vertex to knees) for attenuation correction purposes and to facilitate accurate anatomical localization.
- They will undergo whole-body (skull vertex to knees) PET imaging at 60 minutes. For follow up scans the timing will be as for visit 1 +/- 5 minutes.
- The cannula will be removed at the end of the scan
- The actual dose of [¹⁸F]FPIA administered will be recorded in the study notes.
- AEs will be reportable for up to 24hours after the scan.
- The imaging acquisition will be the same for all [¹⁸F]FPIA PET/CT imaging sessions.

9.3 Radiation dosimetry

The total ionising radiation exposure will be from both PET and CT scans combined. Participants will have three [¹⁸F]FPIA PET/CT scan visits.

Table 3:

Tracer	[¹⁸ F]FPIA	low-dose CT for attenuation Whole Body (skull vertex to knees)
Maximum injected dose per scan	370MBq	
Effective dose (mSv/MBq)	0.0154 mSv/MBq	
Effective dose (mSv)/scan	5.7	6.00
Total Research Protocol Dose (TRPD) (3 PET/CT scan visits)	= 35.1 mSv	

Each patient that participates in this study will have 3 PET/CT scans in addition to their standard of care.

The imaging protocol and associated dosimetry is as per Table 3.

Following an uptake period, the participant will undergo a low dose CT for attenuation correction of PET data (with a dose constraint of 6.0 mSv and image acquisition lasting approximately 30 minutes in total). The radiation dose from 370MBq [¹⁸F]FPIA will be 5.7 mSv (*Dubash et al. 2020*). The maximum additional radiation dose from one [¹⁸F]FPIA PET/CT will be 11.7 mSv.

The maximum Total Research Protocol Dose (TRPD) from this study is therefore 35.1 mSv.

The radiation dose required by the study is additional to routine clinical care.

For comparison, the average annual natural background radiation dose in the UK is 2.3 mSv. The TRPD incurred in this study can be compared to approximately 15.3 years of naturally occurring background radiation exposure.

The risk of developing cancer as a consequence of taking part in this study is estimated as 0.18% (or 1 in 570). For comparison, the natural lifetime cancer incidence in the general population is about 50% (1 in 2).

The radioactive fluorine in the tracer decays by half every 109.7 minutes which means that little will remain in the body by the time the patient leaves the scanning centre.

9.4 Imaging Complications

There are no immediate complications anticipated from the PET/CT scan except for potential mild bruising at the site of insertion of the peripheral cannula which should resolve within a few days. Rarely, the participant may feel dizzy after the scan due to lying flat, but this is normally short lived

Scans will be stopped at any time during the procedure if the subject is unable to tolerate it.

10 ADVERSE EVENTS

10.1 Definitions

Adverse Event (AE): any untoward medical occurrence in a patient or clinical study subject.

Serious Adverse Event (SAE): any untoward and unexpected medical occurrence or effect that:

- Results in death;
- Is life-threatening*;
- Requires hospitalisation or prolongation of existing inpatient's hospitalisation**;
- Results in persistent or significant disability or incapacity;
- Is a congenital abnormality or birth defect;

* "Life-threatening" in the definition of "serious" refers to an event in which the patient was at risk of death at the time of the event; it does not refer to an event which hypothetically might have caused death if it were more severe.

** “Hospitalisation” means any unexpected admission to a hospital department. It does not usually apply to scheduled admissions that were planned before study inclusion or visits to casualty (without admission).

Medical judgement should be exercised in deciding whether an adverse event/reaction is serious in other situations. Important adverse events/reactions that are not immediately life-threatening, or do not result in death or hospitalisation but may jeopardise a patient, or may require intervention to prevent one of the other outcomes listed in the definition above should also be considered serious.

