7 STUDY PROCEDURES

7.1 Table 1 – participant procedures

	-- 28 to 0 days	Scan 1 (Baseline pre-treatment)					Scan 2 (4-6 weeks post treatment) Scan 3 (12 weeks post treatment; +/- 4 weeks)				
		Screening	Pre-PET/CT 120mins	Tracer Dose 0 mins	Low Dose CT	Whole-body PET sweep ⁶ 60 min	Post scan 24 hrs	Pre-PET/CT 120mins	Tracer Dose 0 mins	Low Dose CT	Whole-body PET sweep ⁶ 60 min
Informed Consent	•										
Entry Criteria	•										
Medical History	•										
Treatment History ¹	•	•					•				
Height ² / Weight		•					•				
Pregnancy Test ³		•					•				
WHO Performance status	•										
Renal function eGFR ⁴	•										
Carnitine (blood) ⁵		•					•				
Carnitine (urine) ⁶		•					•				
[¹⁸ F]FPIA injection			•					•			
PET scanning ⁷					•					•	
Adverse events ⁸		•	•	•	•	•	•	•	•	•	•
Tumour Biopsy ⁹		—————→									

1. Cancer treatment history.
2. Repeat Height measurement not required at scans 2 and 3.
3. In women of child bearing potential. On scan day, must be carried out within 2 hours prior to injection of imaging agent.
4. Review of standard of care eGFR bloods taken within 3 months of [¹⁸F]FPIA injection or new sample (≤6mls).
5. Approximately 15 mls
6. Approximately 20mls
7. PET/CT scanning protocol is the same for all scans. Includes low dose CT for anatomical localisation and attenuation correction of the PET data.
8. Adverse events related will be collected for each 24 hour period post each PET/CT scan.
9. A diagnostic tissue biopsy of the primary and/ or metastatic lesion obtained prior to the 1st scan will be retrieved for analysis at any time during study participation.

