7.3.6 Follow Up period

There is no study specific FU following the final research PET/CT. AEs will be reportable for up to 24 hours post each scan. The patients will be assessed and followed up in all routine clinical procedures as per local policy by the treating clinician.

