8.3 Rules for terminating study

The sponsor reserves the right to terminate the study at any time. Prior to dosing of the first subject, the study may be terminated by the sponsor and the investigator without consultation with the Administration of Radioactive Substances Advisory Committee (ARSAC) holder and Ethics Committee. The ARSAC holder, Ethics Committee and Health Research Authority (HRA), must be promptly notified that the study will no longer be taking place and provided with a detailed written explanation. Once dosing with radiopharmaceutical has begun, the study may only be terminated if a careful review of the overall risk benefit analysis demonstrates that the assumptions have changed and that the overall balance is no longer acceptable. The investigators will temporarily halt the study if there has been a SAE which has been judged to be related to the study dosing. In these circumstances, termination can only take place with the agreement of the ARSAC holder and the Ethics Committee.

If it becomes necessary to consider termination of the study after dosing has begun, dosing may be suspended pending discussion between the sponsor, the investigator, the ARSAC holder and the Ethics Committee. Dosing may always be immediately suspended for safety reasons.

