10.2 Reporting of Adverse Events

10.2.1 Non serious AEs

AEs will be collected from the start of each scan visit to up to 24 hours after each PET/CT scan.

Any AEs which remain unresolved at the patient’s last visit in the study should be followed up by the Investigator for as long as medically indicated.

Depending on the nature of the event the reporting procedures below should be followed. Any questions concerning adverse event reporting should be directed to the Chief Investigator in the first instance

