10.2.2 Serious AEs

An SAE form should be sent to the Chief Investigator with 24 hours. However, relapse, death and/or hospitalisations for elective treatment of a pre-existing condition do not need reporting as SAEs.

All SAEs will be reviewed by the Chief Investigator or a designated medically qualified representative to confirm expectedness and causality.

All SAEs should be reported to the relevant REC where in the opinion of the Chief Investigator, the event was:

- ‘Related’, i.e. resulted from the administration of any of the research procedures; and
- ‘Unexpected’, i.e. an event that is not listed in the protocol as an expected occurrence

Reports of related and unexpected SAEs should be submitted within 15 days of the Chief Investigator becoming aware of the event, using the NRES SAE form for non-IMP studies. The Chief Investigator must also notify the Sponsor of all SAEs.

Local investigators should report any SAEs as required by their Local Research Ethics Committee, Sponsor and/or Research & Development Office.

Please send SAE forms to the Sponsor and CI to the below email addresses:

Contact details for reporting SAEs are as follows:

[contact] (Sponsor E-mail)

[contact] (CI E-mail)

[contact] (CI telephone)

Please send SAE forms to the Sponsor and CI on the above email addresses:

(Mon to Fri 09.00 -17.00)

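### The SAE definition in 10.1 requires an event to be unexpected, which contradicts the later expectedness review in 10.2.2 and can keep a serious event out of the reporting chain and the mandatory halt; Table 1 footnote 8 also conflicts with 10.2.1

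*Combined protocol and SAP*

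**What the plan says.** Section 10.1 defines an adverse event broadly: "Adverse Event (AE): any untoward medical occurrence in a patient or clinical study subject". The serious category is narrower in two ways. It begins "Serious Adverse Event (SAE): any untoward and unexpected medical occurrence or effect that" and then lists seriousness criteria, the first of which is death. Section 10.1 does not say what makes an event unexpected.

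Section 10.2.2 covers what happens once an SAE form has been sent: "All SAEs will be reviewed by the Chief Investigator or a designated medically qualified representative to confirm expectedness and causality". Events judged both related and unexpected go to the REC. For that purpose only, unexpected is explained: "i.e. an event that is not listed in the protocol as an expected occurrence". The Sponsor is to be told of all SAEs. The same section says that relapse, death and/or elective hospitalisations for a pre-existing condition need not be reported as SAEs.

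Section 8.3 contains the one mandatory pause: "The investigators will temporarily halt the study if there has been a SAE which has been judged to be related to the study dosing".

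On collecting adverse events, Table 1 footnote 8 reads "Adverse events related will be collected for each 24 hour period post each PET/CT scan". Section 10.2.1 reads "AEs will be collected from the start of each scan visit to up to 24 hours after each PET/CT scan", and 7.3.6 reads "AEs will be reportable for up to 24 hours post each scan".

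**The concern.** Seriousness, relatedness and expectedness are separate judgements. Section 10.1 combines the first and third, so whoever decides whether to send a form must settle expectedness before the role named in 10.2.2 sees the event. If every SAE is unexpected by definition, the expectedness part of the 10.2.2 review has nothing to decide and the second REC criterion is always met.

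The form, the Chief Investigator's review, the Sponsor notification and the mandatory halt all depend on the label SAE. A serious event related to dosing but regarded as expected would lose all four. Section 11.1 describes this as the first use of the tracer in metastatic renal cell cancer, and only 24 evaluable patients are planned, so a single missed serious event could matter.

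Footnote 8 raises a smaller question of the same kind: staff working from Table 1 might record only events they consider related, and only after the scan.

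**Working it through.** The plan gives no figure on this point and no arithmetic applies. The check traces a serious event through 10.1, 10.2.2 and 8.3 as written, then again with the expectedness condition removed from 10.1.

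| Serious event | SAE, form, review and Sponsor: as written | Mandatory halt: as written | SAE, form, review and Sponsor: condition removed | Mandatory halt: condition removed | REC report (either way) |
|---|---|---|---|---|---|
| Related to dosing, unexpected | Yes | Yes | Yes | Yes | Yes |
| Related to dosing, expected | No | No | Yes | Yes | No |
| Not related to any research procedure, unexpected | Yes | No | Yes | No | No |
| Not related to any research procedure, expected | No | No | Yes | No | No |

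1. Both expected rows drop out of the form, the review and the Sponsor notification as written. Only the row that is related and expected also loses the mandatory halt. Section 8.3 asks only for an SAE related to dosing; the expectedness condition enters through 10.1.

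2. The REC column is the same under both wordings, because 10.2.2 already requires both relatedness and unexpectedness.

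3. How many events fall in the expected rows depends on what the word means.
   - On the 10.2.2 meaning, an event is expected only if the protocol lists it. No list carries that label. The nearest text is 9.4, which names mild bruising at the cannula site and, rarely, brief dizziness. Only serious events tied to those are clearly exposed, such as an admission after post-scan dizziness, and even there 9.4 names neither a fall nor an admission.
   - The hospitalisation note in 10.1 uses the word in another sense, contrasting such admissions with planned ones. That sense also removes few events.
   - On the plain meaning, which 10.1 leaves open, a site could omit admissions it anticipates from the cancer or its systemic treatment.

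4. On collection, footnote 8 carries the word related and covers the 24 hours after the scan. The AE definition in 10.1, section 7.3.6 and section 10.2.1 carry no relatedness condition, and 10.2.1 starts at the beginning of the visit. Table 1's own adverse events row is marked in the pre-scan, tracer and scanning columns as well as the post-scan column, so the footnote disagrees with the row it annotates.

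5. As punctuated, 10.2.2 takes relapse and death out of SAE reporting, while 10.1 lists death as making an event serious. The phrase about elective treatment may have been meant to limit the whole list, but the sentence does not say so.

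**The case against.** The strongest reply is that 10.2.2 supplies a meaning for unexpected and that, on this meaning, almost nothing is lost. Toxicities of cancer treatment are not listed in the protocol as expected, so an admission for one would still be an SAE. This stands as a limit on reach. It does not remove the contradiction, because 10.2.2 gives the meaning for REC reporting only and 10.1 does not refer to it.

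Second, asking the Chief Investigator to confirm expectedness presupposes an earlier opinion at the site. That is fair, but an earlier opinion is no reason to withhold the form.

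Third, safeguards exist that do not depend on the SAE label: 8.3 allows dosing to be suspended at once for safety reasons, and 8.2 has the study team review safety data for trends. Both stand, so only the mandatory trigger is lost. Both still rely on events being recorded.

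Fourth, toxicity from cancer treatment would not trigger the 8.3 halt under any SAE definition, since the rule needs a relation to study dosing. That is correct.

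A reader might infer that footnote 8 restricts collection to related events, so that events a site calls unrelated never reach causality review. The documents do not support this. The footnote's word order is garbled, three sections and its own table row contradict it, and 10.2.2 puts no relatedness condition on sending an SAE form.

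**Conclusion.** The point holds as an internal contradiction with a limited safety consequence. Section 10.1 makes expectedness a condition of being an SAE, and 10.2.2 makes sense only if expected SAEs can exist. Read literally, a serious event treated as expected misses the form, the Chief Investigator's review and the Sponsor notification; if it is also related to dosing, it misses the mandatory halt.

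The size cannot be computed, because the documents give no event rates. Reach is small on the 10.2.2 meaning and larger on the plain meaning, and the documents do not show which meaning sites would apply. The conclusion is therefore that serious events could be missed, not that they would be.

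A reader might also measure the problem by the scans done after treatment starts: 24 × 2 = 48 of the planned 24 × 3 = 72 injections in evaluable patients. That counts injections, not lost events, and nothing in the documents says how often serious events at those visits would be called expected.

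Footnote 8 is an unresolved wording conflict and no more. The apparent exemption of death in 10.2.2 is a further conflict with 10.1 in the same reporting chain.

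**What to change.** - In 10.1, delete the words *and unexpected* from the SAE definition. Keep expectedness only in 10.2.2, where it selects events for the REC.
- In Table 1 footnote 8, drop the relatedness wording and use the 10.2.1 rule: all AEs, from the start of the scan visit until 24 hours after the scan.
- Reconcile the 10.2.2 sentence on relapse and death with 10.1, so that the text states plainly whether deaths are reported as SAEs.

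The cost is an edit in three places and a few more SAE forms for the Chief Investigator to review and pass to the Sponsor. The REC reporting criteria do not change. The halt rule in 8.3 needs no rewording; it would apply to any SAE related to dosing, as it already reads.

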10.2 Reporting of Adverse Events

10.2.1 Non serious AEs

AEs will be collected from the start of each scan visit to up to 24 hours after each PET/CT scan.

Any AEs which remain unresolved at the patient’s last visit in the study should be followed up by the Investigator for as long as medically indicated.

Depending on the nature of the event the reporting procedures below should be followed. Any questions concerning adverse event reporting should be directed to the Chief Investigator in the first instance

10.2.2 Serious AEs

An SAE form should be sent to the Chief Investigator with 24 hours. However, relapse, death and/or hospitalisations for elective treatment of a pre-existing condition do not need reporting as SAEs.

All SAEs will be reviewed by the Chief Investigator or a designated medically qualified representative to confirm expectedness and causality.

All SAEs should be reported to the relevant REC where in the opinion of the Chief Investigator, the event was:

- ‘Related’, i.e. resulted from the administration of any of the research procedures; and
- ‘Unexpected’, i.e. an event that is not listed in the protocol as an expected occurrence

Reports of related and unexpected SAEs should be submitted within 15 days of the Chief Investigator becoming aware of the event, using the NRES SAE form for non-IMP studies. The Chief Investigator must also notify the Sponsor of all SAEs.

Local investigators should report any SAEs as required by their Local Research Ethics Committee, Sponsor and/or Research & Development Office.

Please send SAE forms to the Sponsor and CI to the below email addresses:

Contact details for reporting SAEs are as follows:

[contact] (Sponsor E-mail)

[contact] (CI E-mail)

[contact] (CI telephone)

Please send SAE forms to the Sponsor and CI on the above email addresses:

(Mon to Fri 09.00 -17.00)

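### Section 10.1 makes an unexpected occurrence that results in death an SAE, but Section 10.2.2 exempts death from SAE reporting with no limit by cause or relatedness

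*Combined protocol and SAP*

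**What the plan says.** Section 10.1 defines an SAE as an occurrence that is both untoward and unexpected and that meets one of a list of criteria. The first is that it "Results in death". Others include that it "Is life-threatening" or leads to hospitalisation, a term that "means any unexpected admission to a hospital department". A closing paragraph extends seriousness, by medical judgement, to "Important adverse events/reactions that are not immediately life-threatening, or do not result in death or hospitalisation but may jeopardise a patient".

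Section 10.2.2 asks for an SAE form to reach the Chief Investigator within 24 hours. The next sentence gives the exemption: "However, relapse, death and/or hospitalisations for elective treatment of a pre-existing condition do not need reporting as SAEs". The section continues: "All SAEs will be reviewed by the Chief Investigator or a designated medically qualified representative to confirm expectedness and causality". SAEs judged both related to a research procedure and unexpected go to the REC within 15 days. It adds: "The Chief Investigator must also notify the Sponsor of all SAEs".

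Section 8.3 relies on the same judgement: "The investigators will temporarily halt the study if there has been a SAE which has been judged to be related to the study dosing".

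AE collection runs from the start of each scan visit to 24 hours after the scan (Section 10.2.1). Section 7.3.6 and footnote 8 to Table 1 in Section 7.1 give the same 24-hour limit after each scan.

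**The concern.** One section makes a fatal outcome a ground for calling an event serious. The other says that death need not be reported as serious. A site that follows Section 10.2.2 to the letter could send no SAE form for a death, even an unexpected one shortly after a tracer injection.

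The form is the step that puts an event before the Chief Investigator. Without it, nobody may be prompted to ask whether the death was related to a research procedure. The REC report, the notification to the Sponsor and the temporary halt in Section 8.3 all follow from that question. According to Section 11.1 this is the first use of the tracer in metastatic renal cell cancer, and each participant receives it three times. The handling of deaths should therefore not rest on a guess about what the sentence was meant to say.

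What is at stake is participant protection and the completeness of safety reporting.

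**Working it through.** No arithmetic applies. The check sets the sections side by side.

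1. **Does the qualifier in the exemption limit deaths?** The exemption names relapse, death and hospitalisations. Its one qualifier, elective treatment of a pre-existing condition, makes sense for hospitalisations. It cannot sensibly describe a death. Death is therefore exempt without condition.

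2. **Does another section limit it?** Sections 7.3.6, 8.2, 8.3, 10.1 and 10.2.1 contain no statement that the exemption covers only deaths from the disease, or only deaths unrelated to the research. The tests of relatedness and unexpectedness in Section 10.2.2 decide which SAEs go to the REC. They do not decide which deaths get a form.

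3. **Which deaths are in conflict?**
   - *Expected death from the underlying cancer.* Section 10.1 requires the event to be unexpected, so such a death may never meet the definition. For it, the two sections need not conflict.
   - *Death preceded by a recognised serious event.* A life-threatening event, an unplanned admission or a medically important event qualifies on its own ground. The exemption does not remove it, so a form is still due for that event.
   - *Unexpected death with no separately recognised serious event.* Section 10.1 makes the occurrence an SAE through its fatal outcome alone. Section 10.2.2 says that it need not be reported. Here the two sections conflict.

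4. **When does it matter most?** A link to the injection or the scan is most plausible between the start of the scan visit and 24 hours afterwards. The exemption has no exception for that period. Section 9.4 anticipates only mild bruising and, rarely, brief dizziness. A death caused by a research procedure would therefore meet both REC tests in Section 10.2.2, although the same section says that death need not be reported as an SAE.

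5. **What follows if no form is sent?** The exemption removes the duty to report. It does not take death out of the definition in Section 10.1, and the duties to review SAEs and notify the Sponsor stay on the page. The weakness is practical: those duties might not be triggered if the Chief Investigator is never told.

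**The case against.** The strongest reply is that the sentence was meant for deaths from the cancer, and that the word unexpected in Section 10.1 already separates those from the rest. That is probably the intention, and it narrows the conflict. But the limit is not written down, and the deaths left in conflict are the unexpected ones, which most need review.

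A second reply is that other safeguards exist. Section 8.2 provides for review of safety data for trends, a final evaluation at withdrawal and a recorded reason for non-completion. Footnote 8 to Table 1 refers, in unclear wording, to related adverse events. Section 10.2.2 also tells local investigators to report SAEs as their own ethics committee, the Sponsor or the R&D office requires. These lower the chance that a death goes unnoticed. None clearly requires an individual death to be assessed for relatedness, and none removes the contradiction.

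A third reply is that the reporting window is short. That bears on how often the problem could arise. It does not resolve the wording, and the window is where a link to a procedure matters most.

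**Conclusion.** The conflict is real and should be fixed. It concerns unexpected deaths with no separately recognised serious event, above all in the AE reporting window. It rests on reading the exemption as written and on the absence of any limiting text elsewhere. The documents give no basis for estimating how many such deaths to expect. The primary analysis and the sample size of 24 evaluable patients are unaffected.

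A reader might infer more than the documents support:

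- **That every death on study escapes reporting.** Expected cancer deaths may not be SAEs under Section 10.1 at all, and recognised serious events before a death are still reportable.
- **That the gap covers nearly all of the time on study.** This would assume that SAE reporting runs outside the 24-hour post-scan period. Sections 7.1, 7.3.6 and 10.2.1 do not establish that, so no share of time on study is a sound measure of size.
- **That the halt rule in Section 8.3 is contradicted or disabled.** It is neither. It depends on a causality judgement that a missing form might fail to prompt.

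**What to change.** Reconcile Sections 10.1 and 10.2.2. In Section 10.2.2:

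- state which deaths, if any, are exempt from SAE reporting;
- state that the exemption does not cover an unexpected death within the study's AE reporting period, or a death while the participant is on study that the investigator considers possibly related to a research procedure;
- state that these deaths go on an SAE form for causality review.

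No open-ended duty to report later deaths is needed. Sections 7.3.6, 8.1.3 and 8.4 provide no study follow-up after the final scan, apart from resolution of adverse events. Section 8.3 can stay as it is.

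The cost is a short protocol amendment, with the Sponsor and HRA/REC approval described in Section 12.3, and at most a few extra forms.
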